## APPENDIX C. HAMILTON DEPRESSION RATING SCALE-17

### Hamilton Depression Rating Scale (HDRS)

**Reference:** Hamilton M. A rating scale for depression. *J Neurol Neurosurg Psychiatry* 1960; 23:56–62

*Rating* Clinician-rated

*Administration time* 20–30 minutes

*Main purpose* To assess severity of, and change in, depressive symptoms

*Population* Adults

#### Commentary

The HDRS (also known as the Ham-D) is the most widely used clinician-administered depression assessment scale. The original version contains 17 items (HDRS17) pertaining to symptoms of depression experienced over the past week. Although the scale was designed for completion after an unstructured clinical interview, there are now semi-structured interview guides available. The HDRS was originally developed for hospital inpatients, thus the emphasis on melancholic and physical symptoms of depression. A later 21-item version (HDRS21) included 4 items intended to subtype the depression, but which are sometimes, incorrectly, used to rate severity. A limitation of the HDRS is that atypical symptoms of depression (e.g., hypersomnia, hyperphagia) are not assessed (see SIGH-SAD, page 55).

#### Scoring

Method for scoring varies by version. For the HDRS17, a score of 0–7 is generally accepted to be within the normal range (or in clinical remission), while a score of 20 or higher (indicating at least moderate severity) is usually required for entry into a clinical trial.

#### Versions

The scale has been translated into a number of languages including French, German, Italian, Thai, and Turkish. As well, there is an Interactive Voice Response version (IVR), a Seasonal Affective Disorder version (SIGH-SAD, see page 55), and a Structured Interview Version (HDS-SIV). Numerous versions with varying lengths include the HDRS17, HDRS21, HDRS29, HDRS8, HDRS6, HDRS24, and HDRS7 (see page 30).

#### Address for correspondence

The HDRS is in the public domain.

#### Hamilton Depression Rating Scale (HDRS)

PLEASE COMPLETE THE SCALE BASED ON A STRUCTURED INTERVIEW

Instructions: for each item select the one “cue” which best characterizes the patient. Be sure to record the answers in the appropriate spaces (positions 0 through 4).

Statistical Analysis Plan

**1 DEPRESSED MOOD** (*sadness, hopeless, helpless, worthless*)

- 0  Absent.
- 1  These feeling states indicated only on questioning.
- 2  These feeling states spontaneously reported verbally.
- 3  Communicates feeling states non-verbally, i.e. through facial expression, posture, voice and tendency to weep.
- 4  Patient reports virtually only these feeling states in his/her spontaneous verbal and non-verbal communication.

**2 FEELINGS OF GUILT**

- 0  Absent.
- 1  Self reproach, feels he/she has let people down.
- 2  Ideas of guilt or rumination over past errors or sinful deeds.
- 3  Present illness is a punishment. Delusions of guilt.
- 4  Hears accusatory or denunciatory voices and/or experiences threatening visual hallucinations.

**3 SUICIDE**

- 0  Absent.
- 1  Feels life is not worth living.
- 2  Wishes he/she were dead or any thoughts of possible death to self.
- 3  Ideas or gestures of suicide.
- 4  Attempts at suicide (any serious attempt rate 4).

**4 INSOMNIA: EARLY IN THE NIGHT**

- 0  No difficulty falling asleep.
- 1  Complains of occasional difficulty falling asleep, i.e. more than 1/2 hour.
- 2  Complains of nightly difficulty falling asleep.

**5 INSOMNIA: MIDDLE OF THE NIGHT**

- 0  No difficulty.
- 1  Patient complains of being restless and disturbed during the night.
- 2  Waking during the night – any getting out of bed rates 2 (except for purposes of voiding).

**6 INSOMNIA: EARLY HOURS OF THE MORNING**

- 0  No difficulty.
- 1  Waking in early hours of the morning but goes back to sleep.
- 2  Unable to fall asleep again if he/she gets out of bed.

**7 WORK AND ACTIVITIES**

- 0  No difficulty.
- 1  Thoughts and feelings of incapacity, fatigue or weakness related to activities, work or hobbies.
- 2  Loss of interest in activity, hobbies or work – either directly reported by the patient or indirect in listlessness, indecision and vacillation (feels he/she has to push self to work or activities).
- 3  Decrease in actual time spent in activities or decrease in productivity. Rate 3 if the patient does not spend at least three hours a day in activities (job or hobbies) excluding routine chores.
- 4  Stopped working because of present illness. Rate 4 if patient engages in no activities except routine chores, or if patient fails to perform routine chores unassisted.

**8 RETARDATION** (slowness of thought and speech, impaired ability to concentrate, decreased motor activity)

- 0  Normal speech and thought.
- 1  Slight retardation during the interview.
- 2  Obvious retardation during the interview.
- 3  Interview difficult.
- 4  Complete stupor.

**9 AGITATION**

- 0  None.
- 1  Fidgetiness.
- 2  Playing with hands, hair, etc.
- 3  Moving about, can't sit still.
- 4  Hand wringing, nail biting, hair-pulling, biting of lips.

**10 ANXIETY PSYCHIC**

- 0  No difficulty.
- 1  Subjective tension and irritability.
- 2  Worrying about minor matters.
- 3  Apprehensive attitude apparent in face or speech.
- 4  Fears expressed without questioning.

Statistical Analysis Plan

**11 ANXIETY SOMATIC (physiological concomitants of anxiety) such as:**

gastro-intestinal – dry mouth, wind, indigestion, diarrhea, cramps, belching  
cardio-vascular – palpitations, headaches  
respiratory – hyperventilation, sighing  
urinary frequency  
sweating

- 0  Absent.
- 1  Mild.
- 2  Moderate.
- 3  Severe.
- 4  Incapacitating.

**12 SOMATIC SYMPTOMS GASTRO-INTESTINAL**

- 0  None.
- 1  Loss of appetite but eating without staff encouragement. Heavy feelings in abdomen.
- 2  Difficulty eating without staff urging. Requests or requires laxatives or medication for bowels or medication for gastro-intestinal symptoms.

**13 GENERAL SOMATIC SYMPTOMS**

- 0  None.
- 1  Heaviness in limbs, back or head. Backaches, headaches, muscle aches. Loss of energy and fatigability.
- 2  Any clear-cut symptom rates 2.

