## **2.4. Sample Size and Power Considerations**

A sample size of 288 (144 per treatment group) evaluable patients completing the study will provide 90% power to detect a treatment difference of 2 days with a common standard deviation of 5.2 days in changes from the 28-day baseline period in monthly average migraine days between active and placebo groups at a 2-sided alpha level of 0.05. This sample size will provide approximately 80% power to detect a treatment difference of 2 points with a common standard deviation of 6 points in the change from randomization visit (day 1) in HAM-D 17 total score at a 2-sided alpha level of 0.05. Assuming a 15% drop-out rate, approximately 340 patients (approximately 170 patients per treatment group) will be randomized.

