#### **6.3.1.2. Analysis**

The HAM-D 17 total score change from baseline to week 8 will be analyzed using the same MMRM method as described in section 6.2.3.1. The analysis will also be done at weeks 4 and 12.

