##### **6.4.1.2. Analysis**

The PHQ-9 total score change from baseline to weeks 4, 8, and 12 will be analyzed using the same MMRM method as described in section 6.2.3.1, except that the baseline value will not be included in the model.

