## 7. MULTIPLE COMPARISONS AND MULTIPLICITY

A fixed-sequence (hierarchical) testing procedure will be implemented to control the type 1 error rate at 0.05. The primary endpoint will be tested first at a type I error rate of 5%. If the analysis is statistically significant (p-value <0.05), then the key secondary hypothesis will be tested. If not statistically significant, confirmatory hypothesis testing will not be carried out on the remaining hypotheses. This process will repeat accordingly to the order of the secondary endpoints as specified in section 6.3. [REDACTED]

[REDACTED]

[REDACTED]

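### Low-severity improvement: SAP 6.4.4 pools arms and visits in one PHQ-9/migraine-day correlation, and no visible analysis shows what the two headache-naming items contribute to the HAM-D 17 result

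*SAP*

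**What the plan says.** **The correlation.** SAP 6.4.4 specifies a single correlation between change in PHQ-9 total and change in monthly average migraine days. All visits through week 24 and both treatments are combined, in the open-label mITT set. A scatter plot goes with it. For the question of which improvement comes first, the same section plans a graph of mean changes by month and double-blind arm. No interval or p-value is planned for the correlation. Protocol 3.3 makes it an objective to learn whether the drug acts on migraine and depression separately, or whether a gain in one comes first and may bring about the other.

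**The key secondary endpoint.** SAP 6.3.1.2: "The HAM-D 17 total score change from baseline to week 8 will be analyzed using the same MMRM method" as in section 6.2.3.1. It stands directly behind the primary in the SAP 7 sequence: "If the analysis is statistically significant (p-value <0.05), then the key secondary hypothesis will be tested". The HAM-D form in SAP Appendix C names headaches in two items:

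- Item 11, scored 0 to 4, whose heading frames it as the bodily side of anxiety, gives "palpitations, headaches" among its cardiovascular examples.
- Item 13, scored 0 to 2, general somatic symptoms, gives "Heaviness in limbs, back or head. Backaches, headaches, muscle aches", together with loss of energy and fatigability.

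The Appendix C commentary describes the items as "pertaining to symptoms of depression experienced over the past week". The only visible item-level rule for HAM-D is the missing-item rule in SAP 4.3.

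**Cross-checks already planned.** SAP 6.4.1.2: "The PHQ-9 total score change from baseline to weeks 4, 8, and 12 will be analyzed using the same MMRM method", with the baseline value left out of the model. CGI-S is analysed at the same weeks (SAP 6.3.4.2).

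**The concern.** A correlation pooled over arms and visits can be non-zero when no patient's depression follows that patient's migraine. If active treatment lowers both measures, or both fall with time in the study, the pooled points line up. Four visits from one patient are also not four independent observations. The graph by month and arm avoids the pooling but shows group means only, so neither display isolates a patient-level association.

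The HAM-D point is separate, because the correlation uses PHQ-9 and the HAM-D items do not enter it. The trial aims to reduce headache, and headache is named inside its depression endpoint. If the HAM-D total separates, an obvious question is how much of the difference sits in those two items. The item data will exist, but an answer first sought after unblinding would be post hoc.

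**Working it through.** **Reproducing the plan (SAP 2.4; 144 per arm, two-sided 0.05).**

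- Primary, "a treatment difference of 2 days with a common standard deviation of 5.2 days": SE = 5.2 × √(2/144) = 0.613; power = Φ(2/0.613 − 1.96) = 90.4%, against 90% stated.
- HAM-D 17, "a treatment difference of 2 points with a common standard deviation of 6 points": SE = 6 × √(2/144) = 0.707; power = Φ(2/0.707 − 1.96) = 80.7%, against about 80% stated.

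Both reproduce.

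**1. Pooled correlation with no patient-level link.** Assumptions: 288 patients, four visits (months 1, 2, 3 and 6), SD 5.2 days for migraine, and SD 6 borrowed from HAM-D for PHQ-9, for which the documents give no SD. Within each arm and visit the true correlation is zero. Within-patient correlation over time is 0.5 to 0.75.

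| Assumed mean changes, months 1/2/3/6 | Mean pooled r (simulated) |
|---|---|
| Arm difference only: 2 days and 2 points at months 1–3, none at month 6 | about 0.03 |
| Milder trends: migraine placebo −2/−2.5/−3/−5, active −4/−4.5/−5/−5; PHQ-9 placebo −3/−4/−5/−6.5, active −4.5/−5.5/−6.5/−7 | about 0.04 |
| Steeper trends: migraine placebo −1.5/−2.5/−3/−5, active −3.5/−4.5/−5/−5.5; PHQ-9 placebo −2/−4/−5/−8, active −4/−6/−7/−8.5 | about 0.08 |

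Closed-form check for pooling the arms alone: with d₁ = 2/5.2 and d₂ = 2/6, r = (d₁d₂/4) / √[(1 + d₁²/4)(1 + d₂²/4)] = 0.031.

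**If an interval were attached to r.** Under zero association the variance of r is inflated by 1 + 3ρ², where ρ is the within-patient correlation.

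- ρ = 0.5: factor 1.75; correct half-width √1.75 = 1.32 times the naive one; the naive 95% interval covers 0 in 2Φ(1.96/1.32) − 1 = 86% of trials.
- ρ = 0.75: factor 2.69; half-width 1.64 times the naive one; coverage 77%.

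**2. Headache-naming HAM-D items.** Summing the Appendix C item ranges: 9 items × 4 + 8 items × 2 = 52. Items 11 and 13 give 4 + 2 = 6, so at most 6/52 = 11.5% of the range. Item 13 alone is 2/52 = 3.8%. These are ceilings on item range, not amounts of headache content.

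The planned migraine effect is 2 days per 28, or 2 × 7/28 = 0.5 day in a one-week look-back, so small shifts are the plausible ones. The documents give no item-level data. Assume that only these items move:

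- 0.1 point (0.1/0.5 = 0.2 point per migraine day avoided): the chance of a favourable significant total goes from 2.5% to Φ(0.1/0.707 − 1.96) = 3.4%.
- 0.25 point (0.5 point per day avoided): Φ(0.25/0.707 − 1.96) = 5.4%.

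**What extra estimates could show (144 per arm).** Half-width = 1.96 × SD × √(2/144).

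- Sum of items 11 and 13, assumed SD of change 1.0 to 1.5: 0.23 to 0.35 point. The difference detectable with 80% power (2.8 × SE) is 0.33 to 0.49.
- Total of the other 15 items (range 0–46), assumed SD 5 to 6: 1.15 to 1.39 points. This is too wide to reveal shifts of the size above by comparison with the 17-item total.

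**The case against.** The case for leaving the plan alone is substantial, and most of it stands.

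- **Item 11 rates anxiety.** Its heading ties the listed symptoms to anxiety, so only item 13 names headache without that frame. Item 13 also counts fatigue and other aches and reaches its maximum for any clear-cut symptom, so fewer headache days need not lower it. A linear effect per migraine day is therefore an assumption. This keeps the point small.
- **Cross-checks exist.** No PHQ-9 item names headache, and CGI-S asks the rater about mental illness overall. Both are analysed at week 8, and CGI-S is a listed secondary endpoint. They are only partial: PHQ-9 items on sleep, fatigue and concentration can move with migraine. HAM-A is no clean substitute, because one of its items lists tension headache.
- **The pooled r is not labelled a test.** SAP 6.4.4 gives the question of order to the graph, and no interval is planned. The coverage figures above therefore apply only if one is added. What remains is that r as specified cannot carry a patient-level reading.
- **Redaction.** The exploratory endpoints and part of SAP 7 are blacked out, so only the visible text can be judged.

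Three stronger readings are tempting and are not supported:

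- A reader might infer that the overlap inflates the type I error of the key secondary test. It does not: if those items move, the total truly moves.
- A reader might infer that the overlap could produce a positive HAM-D result alone. At the plausible shifts the chance is 3.4% to 5.4%.
- A reader might compute the share of the HAM-D difference carried by the two items and judge it against 11.5%. Nothing in the documents says a mood effect spreads in proportion to item range, and the share is too imprecise. In simulation (2-point effect, true share 11.5%, item SD 1.0 to 1.5, assumed item-total correlation 0.3 to 0.7), the estimated share exceeded 12% in about 42% to 51% of significant trials with no headache excess.

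**Conclusion.** Both points hold as inexpensive improvements of low severity. No stated power, sample size or error rate is wrong, and the primary and key secondary inferences do not change.

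The pooled correlation in SAP 6.4.4 answers a different question from the one in Protocol 3.3. Its numerical artefact is small, about 0.03 to 0.08, and rests on assumed time trends and an SD borrowed from HAM-D. The case for change is that arm, time and patient effects cannot be told apart in one coefficient, not that the coefficient would be badly distorted.

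For HAM-D 17, up to 6 of 52 points lie in items that name headaches among other symptoms, and their contribution is not visibly planned to be shown. The likely contribution is small but unknown, since the documents hold no item-level data.

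**What to change.** **SAP 6.4.4.** Keep the graph. Report the correlation by visit and by double-blind arm. Add one association estimate adjusted for treatment and visit, with clustering by patient, and take any interval only from that model.

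**SAP 6.3.1.2.** Keep the HAM-D 17 total as key secondary. Pre-specify, with no alpha, the week-8 arm difference with 95% CI for the sum of items 11 and 13, and summarise item 13 alone descriptively by arm. The total of the other 15 items may be given as an optional supportive estimate. Set no share calculation and no pass/fail threshold.

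**Cost.** A few sentences and a few tables from data already collected, with no change to endpoint, alpha or sample size. The limits should be stated with the results: at a half-width of about 0.23 to 0.35 point, the item estimate can exclude only a large contribution from these items. The 15-item total also loses genuine fatigue and somatic-anxiety content, so a smaller effect there would not by itself show headache relief.

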**14 GENITAL SYMPTOMS (symptoms such as loss of libido, menstrual disturbances)**

- 0  Absent.
- 1  Mild.
- 2  Severe.

**15 HYPOCHONDRIASIS**

- 0  Not present.
- 1  Self-absorption (bodily).
- 2  Preoccupation with health.
- 3  Frequent complaints, requests for help, etc.
- 4  Hypochondriacal delusions.

**16 LOSS OF WEIGHT (RATE EITHER a OR b)**

- |  |   |
|--|---|
| a) According to the patient:  | b) According to weekly measurements:                       |
| 0  No weight loss.                                       | 0  Less than 1 lb weight loss in week.    |
| 1  Probable weight loss associated with present illness. | 1  Greater than 1 lb weight loss in week. |
| 2  Definite (according to patient) weight loss.          | 2  Greater than 2 lb weight loss in week. |
| 3  Not assessed.   | 3  Not assessed.                          |

**17 INSIGHT**

- 0  Acknowledges being depressed and ill.
- 1  Acknowledges illness but attributes cause to bad food, climate, overwork, virus, need for rest, etc.
- 2  Denies being ill at all.

Total score:

**APPENDIX D. MIGRAINE-SPECIFIC QUALITY OF LIFE  
QUESTIONNAIRE (MSQ) (VERSION 2.1)**

While answering the following questions, please think about *all migraine attacks* you may have had *in the past 4 weeks*.

1. In the past 4 weeks, how often have migraines **interfered** with how well you dealt with family, friends and others who are close to you? (Select only **one** response.)
  - 1  None of the time
  - 2  A little bit of the time
  - 3  Some of the time
  - 4  A good bit of the time
  - 5  Most of the time
  - 6  All of the time
  
2. In the past 4 weeks, how often have migraines **interfered** with your leisure time activities, such as reading or exercising? (Select only **one** response.)
  - 1  None of the time
  - 2  A little bit of the time
  - 3  Some of the time
  - 4  A good bit of the time
  - 5  Most of the time
  - 6  All of the time
  
3. In the past 4 weeks, how often have you had **difficulty** in performing work or daily activities because of migraine symptoms? (Select only **one** response.)
  - 1  None of the time
  - 2  A little bit of the time
  - 3  Some of the time
  - 4  A good bit of the time
  - 5  Most of the time
  - 6  All of the time

Statistical Analysis Plan

4. In the past 4 weeks, how often did migraines **keep you** from getting as much done at work or at home? (Select only **one** response.)

- 1  None of the time
- 2  A little bit of the time
- 3  Some of the time
- 4  A good bit of the time
- 5  Most of the time
- 6  All of the time

5. In the past 4 weeks, how often did migraines **limit** your ability to concentrate on work or daily activities? (Select only **one** response.)

- 1  None of the time
- 2  A little bit of the time
- 3  Some of the time
- 4  A good bit of the time
- 5  Most of the time
- 6  All of the time

6. In the past 4 weeks, how often have migraines **left you too tired** to do work or daily activities? (Select only **one** response.)

- 1  None of the time
- 2  A little bit of the time
- 3  Some of the time
- 4  A good bit of the time
- 5  Most of the time
- 6  All of the time

7. In the past 4 weeks, how often have migraines **limited** the number of days you have felt energetic? (Select only **one** response.)

- 1  None of the time
- 2  A little bit of the time
- 3  Some of the time
- 4  A good bit of the time
- 5  Most of the time
- 6  All of the time

Statistical Analysis Plan

8. In the past 4 weeks, how often have you had to **cancel** work or daily activities because you had a migraine? (Select only **one** response.)

- 1  None of the time
- 2  A little bit of the time
- 3  Some of the time
- 4  A good bit of the time
- 5  Most of the time
- 6  All of the time

9. In the past 4 weeks, how often did you **need help** in handling routine tasks such as every day household chores, doing necessary business, shopping, or caring for others, when you had a migraine? (Select only **one** response.)

- 1  None of the time
- 2  A little bit of the time
- 3  Some of the time
- 4  A good bit of the time
- 5  Most of the time
- 6  All of the time

10. In the past 4 weeks, how often did you have to **stop** work or daily activities to deal with migraine symptoms? (Select only **one** response.)

- 1  None of the time
- 2  A little bit of the time
- 3  Some of the time
- 4  A good bit of the time
- 5  Most of the time
- 6  All of the time

Statistical Analysis Plan

11. In the past 4 weeks, how often were you **not able to go** to social activities such as parties, dinner with friends, because you had a migraine? (Select only **one** response.)
- 1  None of the time
  - 2  A little bit of the time
  - 3  Some of the time
  - 4  A good bit of the time
  - 5  Most of the time
  - 6  All of the time
12. In the past 4 weeks, how often have you **felt** fed up or frustrated because of your migraines? (Select only **one** response.)
- 1  None of the time
  - 2  A little bit of the time
  - 3  Some of the time
  - 4  A good bit of the time
  - 5  Most of the time
  - 6  All of the time
13. In the past 4 weeks, how often have you **felt** like you were a burden on others because of your migraines? (Select only **one** response.)
- 1  None of the time
  - 2  A little bit of the time
  - 3  Some of the time
  - 4  A good bit of the time
  - 5  Most of the time
  - 6  All of the time

Statistical Analysis Plan

14. In the past 4 weeks, how often have you been **afraid** of letting others down because of your migraines? (Select only **one** response.)

- 1  None of the time
- 2  A little bit of the time
- 3  Some of the time
- 4  A good bit of the time
- 5  Most of the time
- 6  All of the time

## **APPENDIX E. SCORING INSTRUCTIONS FOR MSQOL (VERSION 2.1)**

MSQOL (Version 2.1) is a 14-item self-administered questionnaire. Patients are asked to provide responses to each item using a standard six-point Likert type scale. The specific items which make up each dimension are presented in [Appendix D](#).

### **Scoring**

Each of the three MSQOL dimensions is scored independently. For each dimension, a higher score indicates a better health status. The 14 MSQOL items used in scoring are worded with a negative perspective, therefore must be recoded before the dimension scores are calculated.

The scoring of the MSQOL is completed in 3 steps:

1. Recoding of MSQOL items (final item value assignment)
2. Computation of raw dimension scores
3. Transformation of raw dimension scores to a 0 to 100 scale

